9.2 Test and Observation Items and Time Points

9.2.1 Subject characteristics

9.2.1.1 Medical History/Demographic Characteristics

The investigator (or subinvestigator) will identify the following subject demographic characteristics at screening (Days -30 to -2) and record the results in the CRF.

- (1) Sex
- (2) Race
- (3) Date of birth (in AD)
- (4) Height
- (5) Body weight
- (6) Medical history
- (7) History of allergy (including drug allergies)
- (8) Drinking status
- (9) Smoking status

9.2.1.2 Inclusion/exclusion criteria

The investigator (or subinvestigator) will confirm whether each subject meets the inclusion or exclusion criteria at screening and hospitalization (Day -1) and before the first administration, and record the results in the CRF.

9.2.1.3 Serological test

A serological test (HBs antigen, serological test for syphilis, HCV antibody, and HIV antigen/antibody) will be performed at screening. The investigator (or subinvestigator) will record the results in the CRF for fulfillment of the inclusion and exclusion criteria.

9.2.1.4 Drug and alcohol abuse screening

At screening, urinary drug abuse screening (phencyclidines, benzodiazepines, cocaine narcotics, stimulants, hemp, morphine-based anesthesia, barbiturates, tricyclic antidepressants) and breath alcohol test will be conducted. The investigator (or subinvestigator) will record the results in the CRF for fulfillment or not-fulfillment of the inclusion and exclusion criteria.

9.2.1.5 Height, weight, BMI

At the time points shown in the table below, the subjects' height and body weight will be measured to calculate their BMI. The investigator (or subinvestigator) will record the height and body weight in the CRF. The BMI on Day -1 (hospitalization) will be calculated based on the height at screening and body weight on Day -1 (hospitalization).

Test schedule	Screening	Height, weight, BMI
	Day -1 (hospitalization)	Body weight, BMI
	Day X ^a) (hospitalization)	Body weight
	End-of-study assessment or withdrawal	Body weight

a) X = Day of hospital admission in period V
BMI formula: BMI = body weight (kg)/height (m)² (rounded to one decimal place)

Confidential

9.2.2 Concomitant medications

The investigator (or subinvestigator) will confirm whether each subject has used any medications (including commercially available drugs) other than the investigational product, between the start of investigational product administration and completion of the end-of-study assessment. If any, the investigator (or subinvestigator) will record the drug name, dose, unit, route, frequency, duration, and reason for administration in the CRF.

9.2.3 Treatment compliance

The investigator (or subinvestigator) or study collaborator will record the date and time of investigational product administration in the CRF.

9.2.4 Pharmacokinetic assessments

Blood sampling will be performed for measurement of plasma concentrations of unchanged edaravone, sulfate conjugate, and glucuronide conjugate, and urine sampling will be performed for measurement of urine concentrations of them. The investigator (or subinvestigator) or study collaborator will record the dates and times of the blood and urine sampling and the sampled urine volume in the CRF. The measurement will be conducted in the drug concentration measurement site.

If any other assessments are scheduled at the same time point of blood sampling for plasma drug concentration measurement, blood sampling will be performed at the exact scheduled time point, and other assessments will be performed before or after the blood sampling. In principle, a 12-lead ECG and vital signs (except for body temperature) will be measured before the blood sampling for plasma drug concentration measurement and safety assessment. Urine will be forced to void at specified time points.

The acceptable time range for each blood/urine sampling time point will be specified in a separate document.

9.2.4.1 Measurement of plasma concentrations of unchanged edaravone, sulfate conjugate, and glucuronide conjugate

Blood sampling for PK measurement will be conducted at time points shown in the table below.

Day 1	Pre-dose, 0.083, 0.25, 0.5, 0.75, 1, 1.5, 2, 4, 6, 8, 10, and 12 hours post-dose
Day 2	24 and 36 hours post-dose
Day 3	Pre-dose (48 hours post-dose ^{a)} , 0.083, 0.25, 0.5, 0.75, 1, 1.5, 2, 4, 6, 8, 10, and 12 hours post-dose
Day 4	24 and 36 hours post-dose
Day 5	Pre-dose (48 hours post-dose ^{a)} , 0.083, 0.25, 0.5, 0.75, 1, 1.5, 2, 4, 6, 8, 10, and 12 hours post-dose
Day 6	24 and 36 hours post-dose
Day 7	Pre-dose (48 hours post-dose ^{a)} , 0.083, 0.25, 0.5, 0.75, 1, 1.5, 2, 4, 6, 8, 10, and 12 hours post-dose
Day 8	24 and 36 hours post-dose
Day 9	48 hours post-dose ^{a)}
Day X+1 ^{b)}	Pre-dose, 0.083, 0.25, 0.5, 0.75, 1, 1.5, 2, 4, 6, 8, 10, and 12 hours post-dose
Day X+2 ^{b)}	24 and 36 hours post-dose
Day X+3 ^{b)}	48 hours post-dose ^{a)}

a) In the C: Dosing 4 hours after low-fat meal and F: Dosing 4 hours after light meal, blood is collected 46 hours post-dose.

b) X = Day of hospital admission in period V

Frequency of blood sampling: 77

Volume of blood sampling: 5.5 mL/sampling, Total: 423.5 mL

Confidential

[Rationales for setting]

Based on the results of the Phase I clinical pharmacology studies (MT-1186-J01 and MT-1186-J02), time points of blood sampling were set with reference to "Clinical Pharmacokinetic Studies of Pharmaceuticals" [3].

9.2.4.2 Measurement of urine concentrations of unchanged edaravone, sulfate conjugate, and glucuronide conjugate

Urine volume will be measured at voiding and the urine specimen will be processed (see Section 9.2.4.3). The urine is forced to void before administration as well as 24 and 48 hours after administration (46 hours after administration in the conditions C [dosing 4 hours after low-fat meal] and F [dosing 4 hours after light meal]).

9.2.4.3 Processing and storage of specimens

(1) Specimens for measurement of plasma concentrations of unchanged edaravone, sulfate conjugate, and glucuronide conjugate

Promptly after drawing roughly 5.5 mL of blood from the vein into a vacuum tube with heparin sodium, gently invert the tube several times. The subsequent procedures should be performed on ice and completed within 120 minutes after the blood sampling. Transfer the blood into tubes with a stabilizer that has been supplied by the sponsor, and centrifuge the tubes at 4°C, 1,500 g for 10 minutes, so as to complete the centrifugation within 30 minutes after blood sampling. Accurately place the specified amount of plasma into tubes (the primary specimen and backup specimen) with the fixed amount of internal standard, stabilizer, and buffer that has been supplied by the sponsor and store them at -70°C or below. Additional details regarding the procedure are specified in a separate procedure.

Pack the primary specimen and send it in a frozen state with a sufficient amount of dry ice to [REDACTED]. At the request of the sponsor, send the backup specimen, as well.

(2) Specimens for measurement of urine concentrations of unchanged edaravone, sulfate conjugate, and glucuronide conjugate

Collect voluntary urine and measure its volume. Accurately put the specified amount of the urine into test tubes (the primary specimen and backup specimen) containing the fixed amount of stabilizer provided by the sponsor, and store them at -70°C or below. Additional details regarding the procedure are specified in a separate procedure.

Pack the primary specimen and send it in a frozen state with a sufficient amount of dry ice to [REDACTED]. At the request of the sponsor, send the backup specimen, as well.

[Specimen shipping address]
[REDACTED]
[REDACTED]

9.2.5 Safety assessments

The safety assessment period will be between the start of investigational product administration and the completion of the end-of-study assessment (or the completion of withdrawal assessment for subjects withdrawing from the study).

9.2.5.1 Objective findings

The investigator (or subinvestigator) will check for results of all of the following tests without delay.

Confidential

The investigator (or subinvestigator) or study collaborator will record the dates and times of measurement and blood/urine sampling in the CRF.

(1) General laboratory tests

The following test items will be measured. The approximate blood volume per sampling is approximately 2 mL for the following 1), 6 mL for 2), 1.8 mL for 3), and 6 mL for 5), described below. The investigator (or subinvestigator) or study collaborator will provide the sponsor with electronic data on the measurement results (except for the result of coagulation test and hCG) of the subjects who received the investigational product. Blood will be collected in the fasting state.

1) Hematology:

Hemoglobin, hematocrit, red blood cell count, white blood cell count, platelet count, MCH, MCHC, MCV, differential white blood count

2) Biochemistry:

Na, K, Cl, Ca, inorganic phosphorus, urea nitrogen, creatinine, uric acid, total bilirubin, direct bilirubin, ALT, AST, γ -GTP, ALP, LDH, CK, amylase, total cholesterol, triglycerides, LDL-C, HDL-C, total protein, albumin, glucose

3) Coagulation test:

Prothrombin time, activated partial thromboplastin time

4) Urinalysis (qualitative test):

Sediment, qualitative tests (pH, specific gravity, protein, glucose, occult blood, urobilinogen, bilirubin, ketones)

hCG (performed only for female subjects at screening, on Day -1 (hospitalization), and at the end-of-study assessment)

Time points: To be performed in the fasting state at the following time point (before breakfast).

Screening	No specifications
Day -1 (hospitalization)	No specifications
Day 5	Pre-dose
Day 9 (discharge)	Before breakfast
Day X ^{a)} (hospitalization)	No specifications
Day X+3 ^{a)} (discharge)	Before breakfast
End-of-study assessment or withdrawal assessment	No specifications

a) X = Day of hospital admission in period V

Frequency of blood sampling: 7

Total blood sampling volume: 74.6 mL (for details, see "9.3 Blood Sampling Volume")

(2) Vital signs (blood pressure, pulse rate, body temperature)

Systolic and diastolic blood pressure, pulse rate, and axillary body temperature (in Celsius; rounded to one decimal place) of each subject will be measured at the time points shown in the table below. The investigator (or subinvestigator) or study collaborator will record the date, time, and results of the measurement in the CRF.

Systolic and diastolic blood pressure will be measured after at least a 5-minute rest in a lying position. One measurement will be taken for each time point. The measurements will be taken in the same arm throughout the study period, in principle.

If the timing of measurement is the same as that of blood sampling, it should be conducted before blood sampling.

Confidential

Time points

Screening	No specifications ^{b)}
Day -1 (hospitalization)	No specifications ^{b)}
Day 1	Pre-dose, and 1 hour post-dose
Day 2	24 hours post-dose
Day 3	Pre-dose, and 1 hour post-dose
Day 4	24 hours post-dose
Day 5	Pre-dose, and 1 hour post-dose
Day 6	24 hours post-dose
Day 7	Pre-dose, and 1 hour post-dose
Day 8	24 hours post-dose ^{b)}
Day 9 (discharge)	48 hours post-dose ^{b), c)}
Day X ^{a)} (hospitalization)	No specifications ^{b)}
Day X+1 ^{a)}	Pre-dose, and 1 hour post-dose
Day X+2 ^{a)}	24 hours post-dose ^{b)}
Day X+3 ^{a)} (discharge)	48 hours post-dose ^{b), c)}
End-of-study assessment or withdrawal assessment	No specifications ^{b)}

a) X = Day of hospital admission in period V

b) To be performed in the fasting state (before breakfast).

c) In the C: Dosing 4 hours after low-fat meal and F: Dosing 4 hours after light meal, the measurement is conducted 46 hours post-dose.

(3) 12-lead ECG

After at least a 5-minute rest in a lying position, a 12-lead ECG will be recorded at the time points shown in the table below. The investigator (or subinvestigator) will record the date and time of measurement, heart rate, QTcF interval, PR interval, QT interval, RR interval, QRS interval, and findings in the CRF.

If the timing of measurement is the same as that of blood sampling, it should be conducted before blood sampling.

Time points

Screening	No specifications ^{b)}
Day -1 (hospitalization)	No specifications ^{b)}
Day 1	Pre-dose, and 1 hour post-dose
Day 2	24 hours post-dose
Day 3	Pre-dose, and 1 hour post-dose
Day 4	24 hours post-dose
Day 5	Pre-dose, and 1 hour post-dose
Day 6	24 hours post-dose
Day 7	Pre-dose, and 1 hour post-dose
Day 8	24 hours post-dose ^{b)}
Day 9 (discharge)	48 hours post-dose ^{b), c)}
Day X ^{a)} (hospitalization)	No specifications ^{b)}
Day X+1 ^{a)}	Pre-dose, and 1 hour post-dose
Day X+2 ^{a)}	24 hours post-dose ^{b)}
Day X+3 ^{a)} (discharge)	48 hours post-dose ^{b), c)}
End-of-study assessment or withdrawal assessment	No specifications ^{b)}

a) X = Day of hospital admission in period V

b) To be performed in the fasting state (before breakfast).

Confidential

c) In the C: Dosing 4 hours after low-fat meal and F: Dosing 4 hours after light meal, the test is conducted 46 hours post-dose.

(4) Physical examination

At the times shown in the table below, the investigator (or subinvestigator) will examine the subject and record the examination date and findings in the CRF.

Time points

Screening	No specifications
Day -1 (hospitalization)	No specifications
Day 1	Pre-dose, and 1 hour post-dose
Day 2	24 hours post-dose
Day 3	Pre-dose, and 1 hour post-dose
Day 4	24 hours post-dose
Day 5	Pre-dose, and 1 hour post-dose
Day 6	24 hours post-dose
Day 7	Pre-dose, and 1 hour post-dose
Day 8	24 hours post-dose
Day 9 (discharge)	48 hours post-dose ^{b)}
Day X ^{a)} (hospitalization)	No specifications
Day X+1 ^{a)}	Pre-dose, and 1 hour post-dose
Day X+2 ^{a)}	24 hours post-dose
Day X+3 ^{a)} (discharge)	48 hours post-dose ^{b)}
End-of-study assessment or withdrawal assessment	No specifications

a) X = Day of hospital admission in period V

b) In the C: Dosing 4 hours after low-fat meal and F: Dosing 4 hours after light meal, the test is conducted 46 hours post-dose.

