- (18) To assure subject safety, even though there were no toxicity findings at the highest dose of 200 mg/kg in the reproductive and developmental toxicity studies.
- (19) To perform the study safely and ethically.

Confidential

4. Explanation and Informed Consent

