5.2.2 Study Period and Evaluation Period

Study period:

The study period is defined as the period from the time of obtaining the informed consent to the time of completion of the end-of-study assessment or discontinuation assessment (for subjects who have entered into the follow-up period, to the time of completion or termination of the follow-up).

Screening:

Subjects providing informed consent will be screened for eligibility to select subjects meeting all of the inclusion criteria and none of the exclusion criteria (16 subjects with a few reserve subjects).

Confidential

Evaluation period: The evaluation period is defined as the period from completion of dosing of the investigational product on Day 1 to completion of the end-of-study assessment or discontinuation assessment. The duration of hospitalization will be 10 days and 9 nights (Day -1 to Day 9) for Period I to Period IV, and 4 days and 3 nights (Day X to Day X+3) for Period V.

End-of-study assessment: The prespecified observations and tests will be performed as the end-of-study assessment, 7 days (± 2 days) after the last dose of the investigational product.

[Rationales for setting]

A crossover design was selected for this study in order for PK parameters to be precisely compared in a small number of subjects in accordance with the "Partial Revision of Guidelines including the Guideline for Bioequivalence Studies of Generic Products" (PFSB/ELD Notification No. 0229-10 dated February 29, 2012) [1] and the Guidance for Industry: Bioavailability and Bioequivalence Studies Submitted in NDAs or INDs - General Considerations (March 2014) [2].

The duration from discharge in period IV to admission in period V was set to 11-18 days as the duration necessary to obtain PK results from period I to IV.

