8.6.2 Instruction for Daily Life

The investigator (or subinvestigator) or study collaborator will instruct the subjects to follow the points below.

- (1) The subjects will not receive or donate blood after providing informed consent until completion of the end-of-study assessment.
- (2) The subjects will not engage in strenuous exercise from 7 days before the start of the first administration until completion of the end-of-study assessment.
- (3) The subjects will reduce their physical burdens by refraining from excessive eating and drinking, and by having enough sleep from 7 days before the start of the first administration until completion of the end-of-study assessment.

Confidential

- (4) The subjects will not have an excessive amount of foods and drinks containing alcohol (>32 g/day, as absolute alcohol) throughout the period from screening to completion of the end-of-study assessment, except for the period indicated in section "8.5.1 (2)."
- (5) If a subject experiences any abnormal symptom occurs after providing informed consent until the completion of the end-of-study assessment, the subject will promptly report to the investigator (or subinvestigator) or study collaborator.
- (6) The subjects must report to the investigator (or subinvestigator) or study collaborator, in advance if they use any drug that is prescribed by a doctor who is not involved in this study or that is purchased from a drugstore, or if they are planning to use a new drug after providing informed consent until completion of the end-of-study assessment.
- (7) The investigator (or subinvestigator) or study collaborator will instruct female subjects to use an effective method of contraception, as described below, from screening or 2 weeks before the start of investigational product administration, whichever comes earlier, to 14 days after the completion (or discontinuation) of the administration, and male subjects to do so from the start of investigational product administration to 14 days after the completion (or discontinuation) of the administration.
 - 1) Abstinence (not having sexual intercourse)
 - 2) Use of two effective methods of contraception.
Combination use of a barrier method (latex condoms for men or vaginal pessaries) and a more effective method (e.g., oral contraceptives or vaginal rings) is recommended. The male subjects' female partners also need to use an effective method of contraception (e.g., vaginal pessaries, oral contraceptives, or vaginal rings).

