Urine sampling for edaravone ^{d)}		←												→				

- a) The diet menu in period V will be determined based on the PK data collected from period I to IV.
- b) The dosing time after a meal in period V will be determined based on the PK data collected from period I to IV.
- c) Assess serious adverse events beginning after informed consent is obtained. Survey of other adverse events will be started after administration of the investigational product is started.
- d) Urine volume is measured for each void. A portion of the urine is collected, dispensed into a tube containing stabilizer, and stored frozen. The urine is forced to void at 24-hour intervals.
- e) At the time of withdrawal, the same tests will be performed as those of the end-of-study assessment.
- f) In the F: Dosing 4 hours after light meal, tests/observations are conducted 46 hours after administration of the investigational product.

Confidential

Test items	Description
Demographic and other baseline characteristics (subject characteristics)	Sex*, race*, date of birth*, body height*, body weight, BMI**, medical history*, complications*, history of allergies (including drug allergies) *, alcohol consumption*, smoking status*
Interview/physical examination	Interview and physical examination
Vital signs	Blood pressure (supine), pulse rate, body temperature (axillary)
12-lead ECG	HR, QTcF interval, PR interval, QT interval, RR interval, QRS interval, findings
Laboratory tests	Hematology
	Hemoglobin, hematocrit, red blood cell count, white blood cell count, platelet count, MCH, MCHC, MCV, differential white blood count
	Biochemistry
	Na, K, Cl, Ca, inorganic phosphorus, urea nitrogen, creatinine, uric acid, total bilirubin, direct bilirubin, ALT, AST, γ -GTP, ALP, LDH, CK, amylase, total cholesterol, triglycerides, LDL-C, HDL-C, total protein, albumin, glucose
Coagulation test	Prothrombin time, activated partial thromboplastin time
	Urinalysis
Serological tests*	HBs antigen, serological test for syphilis, HCV antibody, HIV antigen/antibody
Drug/alcohol abuse screening*	Urine drug abuse screening (phencyclidine, cocaine, barbiturates, tetrahydrocannabinol, benzodiazepines, amphetamine/methamphetamine, morphine-based anesthesia), measurement of breath alcohol level

*: To be performed only at screening.

**: To be performed at screening and Day -1 (hospitalization).

***: To be performed only for female subjects. At screening, on Day -1, (hospitalization) and at the end-of-study assessment.

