11.2 Pregnancy Report

If the investigator (or subinvestigator) becomes aware of the pregnancy of a female subject or a male subject's female partner, and that her embryo or fetus may be exposed to the investigational product before completion of the contraception period, the investigator (or subinvestigator) shall promptly report to the sponsor using the Pregnancy Report in Appendix 1. If the female subject or the female partner wishes to give birth to the child, the investigator (or subinvestigator) will follow up on her delivery, as much as possible, and assess whether or not there are any effects on the newborn. The investigator (or subinvestigator) will report the results, in detail, to the sponsor using the Pregnancy Report in Appendix 1.

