12.1 Criteria for Subject Withdrawal

A subject will be withdrawn from the study if any of the following criteria are met.

- (1) The subject requests to withdraw from the study.
- (2) The subject is determined to be clearly ineligible as a study subject.
- (3) Study continuation becomes difficult for the subject due to the onset of an AE.
- (4) Other cases where the investigator (or subinvestigator) judges that the subject should be withdrawn from the study.

[Rationales for setting]

These criteria were established to perform the study ethically and to ensure the safety of the subjects.

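### No pregnancy test before the Period V dose: the last hCG result is 21 to 28 days old when women are dosed after 11 to 18 days at home (minor)

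*Protocol*

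**What the plan says.** Women are eligible (Protocol 3.2). Section 9.2.5.1 lists hCG under urinalysis and sets its timing: "hCG (performed only for female subjects at screening, on Day -1 (hospitalization), and at the end-of-study assessment". The footnote to the test-item table in section 9.1 gives the same three occasions: "To be performed only for female subjects. At screening, on Day -1, (hospitalization) and at the end-of-study assessment". The protocol summary repeats that footnote. The Period V schedules (protocol summary 9, Protocol 9.1, SAP 3.3) carry a single pregnancy-test mark, which fits the end-of-study visit.

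The first admission runs from Day -1 to Day 9 and the second from Day X to Day X+3, with the fifth dose on Day X+1. Section 5.2.2 states the interval: "The duration from discharge in period IV to admission in period V was set to 11-18 days".

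Eligibility is confirmed at set times only. Under section 9.2.1.2 the investigator checks whether each subject "meets the inclusion or exclusion criteria at screening and hospitalization (Day -1) and before the first administration". No recheck is stated before Period V.

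Section 8.6.2 (7) requires abstinence or two contraceptive methods, starting for women "from screening or 2 weeks before the start of investigational product administration, whichever comes earlier" and continuing to 14 days after dosing ends. The rationale for the pregnancy exclusion in section 3.3 begins "To assure subject safety, even though there were no toxicity findings at the highest dose of 200 mg/kg". Section 11.2 makes a pregnancy reportable when "her embryo or fetus may be exposed to the investigational product before completion of the contraception period".

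**The concern.** The protocol means to keep pregnant women from being dosed, and it kept testing in place despite negative reproductive toxicology. Yet for one of the five doses the latest pregnancy result predates the whole first admission and a further 11 to 18 days at home. On Day X the protocol repeats weight, physical examination, vital signs, ECG and the laboratory tests, but not hCG. Interview and examination can bring out a pregnancy the woman knows about, but not one she does not. The end-of-study test can only show an exposure that has already happened.

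The matter is one of subject safety. It has no bearing on the food-effect estimates, except that a subject found pregnant would not contribute to Period V.

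The argument does not depend on treating Day X like Day -1. The Day -1 test can also catch a conception from before contraception began, whereas the gap lies wholly inside the contraception period. What is left uncovered is contraceptive failure or non-adherence, mainly during the gap.

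**Working it through.** **Day count.** Protocol 5.2.2 describes Day -1 to Day 9 as 10 days and 9 nights. That holds only if there is no Day 0; with a Day 0 the stay would be 11 days and 10 nights. So Day n falls n days after Day -1.

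**Inputs.** Discharge on Day 9; gap 11 to 18 days; Period V dose on X+1; end-of-study assessment 7 ± 2 days after the last dose (all Protocol 5.2). The SAP gives the Period V dose as Day 23 (7.1.2.1, adverse event periods) or Day 24 (9.3, analysis visits). The two SAP tables disagree by a day, so both are carried.

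**Formulas.** Day X = 9 + gap. Dose = X + 1. Last hCG to dose = X + 1 days. Test to test = (X + 1) + 5 up to (X + 1) + 9.

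| Case | Gap (days) | Day X | Dose day | Last hCG to dose (days) | Dose to next hCG (days) | Test to test (days) |
|---|---|---|---|---|---|---|
| Protocol, shortest | 11 | 20 | 21 | 21 | 5–9 | 26–30 |
| SAP 7.1.2.1 | 13 | 22 | 23 | 23 | 5–9 | 28–32 |
| SAP 9.3 | 14 | 23 | 24 | 24 | 5–9 | 29–33 |
| Protocol, longest | 18 | 27 | 28 | 28 | 5–9 | 33–37 |

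If 11 to 18 is read as full days strictly between discharge and admission, the interval from last hCG to dose becomes 22 to 29 days. The conclusion does not change.

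**What a Day X test would catch.** The documents give no lag from conception to a positive urine hCG; 7 to 14 days is assumed here. The detectable part of the gap is max(0, gap − lag):

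| Gap (days) | Lag 7 days | Lag 14 days |
|---|---|---|
| 11 | 4 | 0 |
| 13 | 6 | 0 |
| 14 | 7 | 0 |
| 18 | 11 | 4 |

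A Day X test would also find a conception too recent to show on Day -1, because Day X is 20 to 27 days later. That woman would already have had four doses, and only the fifth would be prevented.

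**Whether it needs blood.** The section 9.2.5.1 blood total is 74.6 mL. From section 9.3, serology 6 + hematology 14 + biochemistry 42 + coagulation 12.6 = 74.6 mL. Nothing is left over for hCG, which agrees with its listing under urinalysis. Urinalysis is already among the laboratory tests scheduled on Day X, the day before dosing.

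**The case against.** The strongest reply is that nothing here is an error. The documents agree on three test occasions, and no requirement in them is breached. Several controls already apply: contraception throughout, exclusion of women planning pregnancy, interview and examination on Day X and before the X+1 dose, withdrawal where "The subject is determined to be clearly ineligible as a study subject" or the investigator so judges, an end-of-study hCG, and pregnancy reporting. The 21 to 28 days also include the inpatient stay; time at home is only 11 to 18 days.

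The expected yield is small. Assume, beyond the documents, that all 16 subjects are women, that annual contraceptive failure is 1 to 10%, and that the gap is 14 days. Expected conceptions in the gap are then 16 × 0.01 × 14/365 = 0.006 to 16 × 0.10 × 14/365 = 0.06 per study. With 0 to 7 of those 14 days detectable, a Day X test would find 0 to 0.03. With 11 detectable days in an 18-day gap, the upper figure is 16 × 0.10 × 11/365 = 0.05. The remedy also touches several sections and needs investigator agreement and IRB approval.

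Most of this stands and sets the severity. It does not remove the gap. Interview and examination cannot detect an unrecognised pregnancy, and the withdrawal criteria cannot act on a result that does not exist. Contraception is a strong safeguard but not a complete one. The protocol also blurs it: section 8.6.2 recommends pairing a barrier with, for example, oral contraceptives, while sections 3.3 (13) and 8.5.1 restrict all drugs other than acetylsalicylic acid, unless the investigator finds them necessary.

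**Conclusion.** The point holds, at minor severity. No pregnancy test precedes the Period V dose. That dose falls 21 to 28 days after the last test (23 to 24 on the SAP's schedule), and the next test follows 5 to 9 days later. These figures rest only on the protocol's own day numbering and intervals.

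The risk to subjects is low, for the reasons the protocol itself supplies: required contraception, no reproductive toxicity findings at 200 mg/kg, and a single 105 mg exposure. The benefit of testing on Day X is less certain than the gap itself. It depends on the assumed 7 to 14 day detection lag and on the number of women enrolled, which the documents do not state. The case for acting is that the check serves the protocol's stated safety aim and costs almost nothing.

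**What to change.** Add urine hCG for female subjects to the urinalysis already scheduled on Day X, and require a negative result before the Day X+1 dose. Amend section 9.2.5.1, the Period V schedules (protocol summary 9, Protocol 9.1, SAP 3.3) and the test-item footnote on pregnancy testing. In section 12.1, name a positive hCG as a withdrawal criterion, with reporting under section 11.2. Exclusion criterion (18) can stay as it is, because it governs entry.

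The cost is protocol wording, with the usual agreement and IRB approval, and one urine hCG per woman on a sample already collected. No visit or blood draw is added. A subject found pregnant would be lost from Period V. With the change, the last test before the fifth dose would be 1 day old instead of 21 to 28 days old.
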